Efficacy Assessments

Blood samples for determination of plasma HIV-1 RNA viral load and immunologic parameters and for HIV-1 genotypic/phenotypic resistance testing (PhenoSense GT® Plus Integrase) will be taken at the time points specified in the Schedule of Assessments (SoA).

Plasma viral load will be measured using a validated assay at a central laboratory (ie, Roche COBAS AmpliPrep/COBAS TaqMan HIV-1 Test, Version 2.0.) The assay linear range is 20 to 10,000,000 copies/mL with a lower limit of quantification (LLOQ) of 20 copies/mL and a limit of detection (LOD) of 20 copies/mL). Immunologic change will be determined by changes in CD4+ cell count (absolute and %). Changes in viral load, changes in CD4+ cell counts (either decreases or increases) or detected resistance will be part of the efficacy analysis and should not be reported as AEs or SAEs.

Participants will be considered to have virologic rebound if they have 2 consecutive HIV-1 RNA values ≥200 copies/mL at a scheduled or unscheduled visit after maintaining HIV-1 RNA <50 copies/mL; confirmatory testing should be conducted 2 to 4 weeks after the initial HIV-1 RNA value ≥200 copies/mL. For participants with confirmed virologic rebound, HIV-1 genotypic and phenotypic resistance testing (PhenoSense GT® Plus Integrase) will be performed on the confirmed rebound sample, if HIV 1 RNA ≥400 copies/mL or on a following visit with HIV-1 RNA ≥400 copies/mL. Genotype/phenotype testing at other time points may be requested if deemed necessary by the sponsor.

Adherence

Treatment adherence for the study will be assessed at all study visits by participant self-report using a 4-day recall.

Safety Assessments

Safety will be evaluated throughout the study from the time a signed and date ICF is obtained until completion of the participant's last study-related activity. The study will include following evaluations of safety:

- AEs;
- Clinical laboratory tests (biochemistry, hematology, urinalysis, urine chemistry);
- Vital signs measurements;
- Physical examination (complete or symptom directed).

Patient Reported Outcomes:

Patient reported outcomes, including the BSQ-8D, DAILY EATS, HIV-SI, and PGIC (including PGIC-S) will be completed.

Pharmacokinetic Assessments

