If a participant discontinues study intervention for any reason except for withdrawal of consent before the end of the study, ESID assessments should be obtained as soon as possible but no later than 1 week of discontinuing study intervention. For participants who discontinue study intervention for any reason and have HIV-1 RNA \geq 400 copies/mL at the last viral load measurement, the ESID assessments will also include genotypic and phenotypic resistance testing (using PhenoSense GT® Plus Integrase). In case of early discontinuation, an HIV-1 resistance report will be forwarded to the participant's primary care provider to assist in the selection of a new ARV regimen. If the reason for withdrawal from the study is withdrawal of consent, then no additional assessments are allowed.

D/C/F/TAF FDC assigned to the participant who discontinued D/C/F/TAF FDC may not be assigned to another participant. Additional participants will not be entered.

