9.4.3.2. Resistance/Efficacy Analyses

HIV-1 genotypes, and phenotypes (PhenoSense GT^{\otimes} Plus Integrase) if applicable, will be analyzed from samples of participants with virologic rebound and with HIV-1 RNA \geq 400 copies/mL.

The proportion of virologic suppression (HIV-1 RNA<50 copies/mL) and failure (HIV-1 RNA ≥50 copies/mL) using the FDA snapshot algorithm in the ITT will also be analyzed as a secondary endpoint at Weeks 24 and 48 using descriptive statistics along with 95% confidence interval (CI, Wilson score method).

The proportion of participants experiencing virologic rebound through Week 24 and 48 will be tabulated using descriptive statistics along with the 95% confidence intervals (CI, Wilson score method).

The changes from screening/baseline in CD4⁺ cell count at Weeks 24 and 48 will be summarized using descriptive statistics.

The number of identified protease (PR) mutations (including International AIDS Society [IAS]-USA primary and secondary PI resistance-associated mutations [RAMs], reverse transcriptase (RT) mutations (including IAS-USA nucleoside/nucleotide RT inhibitor [N[t]RTI] RAMs, IAS-USA non-nucleoside RT inhibitor [N[t]RTI] RAMs), and integrase (INI) mutations (including International AIDS Society [IAS]-USA INI-RAMs and IAS-USA primary INI mutations), as well as specific mutations associated with resistance to DRV, FTC, and TAF, will be tabulated based on the observed virologic rebound through the study period. Retrospectively, fold change (FC) in 50% effective concentration (EC₅₀) of ARVs may be analyzed and tabulated dependent on the number of virologic rebounds and phenotypes available through the study period.

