Virologic failure leading to discontinuation will be determined by a medical assessment of the comment fields and other specification reasons for discontinuation to determine if anyone discontinued the trial due to lack of efficacy reasons. Upon further clinical evaluation additional comments or other specification reasons might need to be added, and these will be documented in the DPS. An identified subject will be classified to the snapshot categories as follows:

- Data within window: If an identified subject has HIV RNA data within the window, the HIV RNA data will be used to classify the subject as either at or above the threshold or below the threshold.
- No data within window: If an identified subject does not have HIV RNA data in window, then
 regardless of the last HIV RNA value the subject will be classified as "Virologic failure leading to
 discontinuation".

Virologic response will then be categorized as follows: Yes (virologic response), or No (virologic failure and no viral load data in the Week 24 visit window and Week 48 visit window).

The snapshot approach will also be displayed over time by analysis time points and will follow the same logic as defined above weeks 24 and 48 time point. (Please see Section 2.2. Visit Windows for visit intervals).

Subjects will also be classified as confirmed virologic rebounds if they meet the criteria below:

• Two consecutive HIV RNA ≥200 copies/mL at a scheduled or unscheduled visit after maintaining HIV-1 RNA <50 copies/mL).

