
Efficacy:

- Proportion of participants with confirmed virologic rebound through Week 24 and Week 48, respectively.
- Proportion of participants with virologic response (HIV-1 RNA<50 copies/mL) at Week 24 and Week 48, respectively, according to the FDA snapshot algorithm
- Proportion of participants with virologic failure (HIV-1 RNA ≥50 copies/mL) at Week 24 and Week 48, respectively, according to the FDA snapshot algorithm
- Proportion of participants having virologic response (HIV-1 RNA<200 copies/mL) at Week 24 and Week 48, respectively, according to the FDA snapshot algorithm
- Proportion of participants having virologic failure (HIV-1 RNA ≥200 copies/mL) at Week 24 and Week 48, respectively, according to the FDA snapshot algorithm
- Change from Baseline in CD4+ cell count at Week 24 and Week 48 respectively.

Resistance:

- Proportion of participants with baseline DRV, FTC, TFV and INI resistance-associated mutations (RAMs) based on historical genotypes.
- Incidence of observed genotypic and phenotypic ARV resistance for participants meeting HIV-1 RNA rebound criteria through Weeks 24 and 48, respectively.
- Proportion of participants with newly identified post-baseline RAMs and phenotypic resistance compared to pre-baseline resistance tests when available, upon meeting confirmed virologic rebound through Weeks 24 and 48, respectively.

PROs:

- Change from Baseline in the proportion of participants who have bothersome symptoms (scores of 2, 3 or 4) across all items of the HIV-SI at Week 24 and Week 48, respectively.
- Change from Baseline in the proportion of participants who have any symptoms (scores of 1, 2, 3 or 4) across all items of the HIV-SI at Week 24 and Week 48, respectively.
- Association between treatment arm and each bothersome symptom of the HIV-SI adjusting for Baseline variables at Week 24 and Week 48, respectively.
- PGIC and PGIC-S at Week 24 and Week 48, respectively.

Adherence:

• Adherence rates by participant self-report using 4-day recall at Weeks 4, 12, 24, 36 and 48, respectively.

Exploratory:

Exploratory clinical biomarker:

• Change from Baseline in alpha melanocyte-stimulating hormone at Week 24 and Week 48, respectively.

Exploratory PROs:

- Change from Baseline in the scores on the DAILY EATS at Week 24 and Week 48, respectively.
- Change from Baseline in the scores on the BSQ-8D at Week 24 and Week 48, respectively.

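### Resistance found at early discontinuation in a participant whose viral load rise was not confirmed enters no planned endpoint, although Protocol 7.1 orders the test

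*SAP*

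**What the plan says.** **Testing rule.** Under Protocol 7.1, for participants who stop study intervention for any reason with HIV-1 RNA at or above 400 "copies/mL at the last viral load measurement, the ESID assessments will also include genotypic and phenotypic resistance testing". No second sample is required. Withdrawal of consent is the exception, since no further assessments are then allowed.

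**Rebound rule.** SAP 6.1.2 defines confirmed rebound as "Two consecutive HIV RNA ≥200 copies/mL at a scheduled or unscheduled visit after maintaining HIV-1 RNA <50 copies/mL". The protocol synopsis has the same two-sample rule and says the confirmatory test should come 2 to 4 weeks after the first value.

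**Endpoints.** SAP 6.2.1 lists "Proportion of participants with confirmed virologic rebound through Week 24 and Week 48, respectively" for rebound. For resistance it lists "Incidence of observed genotypic and phenotypic ARV resistance for participants meeting HIV-1 RNA rebound criteria through Weeks 24 and 48, respectively", and the proportion with newly identified mutations and phenotypic resistance "upon meeting confirmed virologic rebound through Weeks 24 and 48, respectively". SAP 6.2.1.1 and Protocol 3.1 and 3.2 carry the same restriction. In Protocol 9.4.3.2, genotypes and phenotypes "will be analyzed from samples of participants with virologic rebound and with HIV-1 RNA" of at least 400 copies/mL. SAP 6.2.2.2.1 plans testing for confirmed rebounders and leaves other time points to discretion.

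**Data cut-off.** SAP 2.4.1.1 includes efficacy data only up to the last dose of randomized treatment. The ESID visit may take place up to 1 week after stopping.

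**The concern.** The testing rule covers people whom the analysis rule leaves out. Someone who stops with a single value of 400 copies/mL or more is tested for resistance under Protocol 7.1. Unless a second value of at least 200 is on record, the result belongs to no endpoint in either document.

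These people left while viraemic, so the reason they go uncounted is close to the outcome itself. Each omission can only lower the number of participants reported with resistance. One case could matter to the reader: Protocol 2.2 reports a single D/C/F/TAF participant with emergent FTC resistance in the Phase 3 studies, so a single omitted genotype could be the difference between resistance observed and none observed.

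**Working it through.** The plan states no figure on this point, so the check is mainly a comparison of texts.

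**1. Rules side by side**

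| Place | Covers | Viral load needed |
|---|---|---|
| Protocol 7.1 | Anyone who discontinues study intervention, consent not withdrawn | One value ≥400, the last measured |
| SAP 6.1.2 | Confirmed rebound | Two consecutive values ≥200 after <50 |
| SAP 6.2.1, 6.2.1.1; Protocol 3.1, 3.2 | Post-baseline resistance endpoints | Rebound criteria met |
| Protocol 9.4.3.2 | Resistance analysis | Rebound, and ≥400 |
| SAP 6.2.2.2.1 | Resistance testing | Confirmed rebound, and ≥400; otherwise discretionary |

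The first row is wider than the others. The difference is discontinuers with a last value ≥400 and no second consecutive value ≥200.

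**2. Can the value be confirmed?**
- *Prior visit and ESID both ≥200.* These are two consecutive values, and SAP 6.1.2 sets no minimum interval. The participant is a confirmed rebounder if the ESID value counts. Under SAP 2.4.1.1 a sample drawn after the last dose may not. Footnote a to the visit-window table in SAP 2.2 points the other way: it assigns data from an early-discontinuation visit to a time interval. The SAP does not settle which applies.
- *First elevation at ESID.* Confirmation needs a later sample. The Schedule of Activities asks for a retest 2 to 4 weeks after any result ≥50 becomes available and does not exempt ESID. However, participants return to routine care at ESID, the 30-day visit is required only for an ongoing adverse event, and the retest would fall after the last dose.

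**3. What the snapshot endpoints catch (SAP 6.1.2)**
- A value ≥50 or ≥200 inside the window (Weeks 18-30 or 42-54): failure at that threshold.
- Left for a reason other than adverse event, death or virologic failure, last value ≥50 or ≥200: failure.
- Left because of virologic failure, no value in the window: failure.
- Left for an adverse event or death before the window: missing-data category, whatever the HIV-1 RNA.

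Only the last group, if unconfirmed, is counted neither as rebound, nor as resistance, nor as snapshot failure. The snapshot table holds no resistance data for anyone.

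**4. Size**

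Inputs: 55 per arm (Protocol 9.2); maximum 150 in total after sample size re-estimation, so 150/2 = 75 per arm. The number of unconfirmed viraemic leavers is not given; I assume 0 to 3 per arm.

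One participant is 1/55 = 1.8 percentage points, or 1/75 = 1.3 at the maximum size. Starting, for illustration, from one confirmed rebound in 55:

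| Unconfirmed leavers added | Rate | Wilson 95% CI |
|---|---|---|
| 0 | 1/55 = 1.8% | 0.3 to 9.6 |
| 1 | 2/55 = 3.6% | 1.0 to 12.3 |
| 2 | 3/55 = 5.5% | 1.9 to 14.9 |
| 3 | 4/55 = 7.3% | 2.9 to 17.3 |

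For scale, Protocol 2.2 cites 2.5% rebound at Week 48 in the earlier switch study: 0.025 × 55 = 1.4 expected in an arm of 55, with probability 0.975^55 = 0.25 of none. One leaver is about as large as the whole expected count.

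**The case against.** The case against has real weight.

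- **Confirmation is possible.** A reader might infer that a high value at the last visit or at ESID can never be confirmed. The documents do not support that: HIV-1 RNA is drawn at ESID, a retest is requested, and unscheduled visits are allowed. What stands is that confirmation may not happen and that the last-dose cut-off may discard it.
- **Rebound is mostly covered.** A reader might infer that these participants vanish from the virology results. They do not. They stay in the ITT denominator as non-rebounders, and the snapshot endpoints count most as failures on one value. The exception is exit for an adverse event or death before the window.
- **The test may be for care only.** Protocol 7.1 sends the resistance report to the primary care provider to help choose the next regimen. Ordering a test for care without making it an endpoint is not a contradiction. Even so, a resistance summary that may omit resistance found on study is incomplete.
- **The SAP follows the protocol.** This is correct. The SAP does not depart from the protocol's endpoints; the gap between Protocol 7.1 and the analysis lies in both documents.
- **Few people are involved.** Protocol 2.1 gives adverse event discontinuation below 2%. If that were independent of a 2.5% rebound rate, 55 × 0.02 × 0.025 ≈ 0.03 viraemic adverse event leavers per arm would be expected. Independence is an assumption, dependence would raise the figure, and it leaves out other reasons for stopping. The group is nevertheless likely to be small.
- **The endpoints are secondary and descriptive.** This is also correct, and it limits the consequence.

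**Conclusion.** The gap holds for resistance. As written, a result that Protocol 7.1 orders can fall outside every planned resistance endpoint, and the number of participants reported with resistance, or their share of the arm, can only be lowered. For rebound the point is narrower: confirmed rebound is a legitimate stated choice, and only leavers for an adverse event or death before the window escape both it and snapshot failure.

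This rests on the SAP being followed literally, without the discretionary extra analyses, and on resistance counting as efficacy data, as Protocol 8.1.3.1 treats it. The 1.8 points is the weight of one participant in an arm of 55. It should not be read as an estimate of bias, because the documents give no frequency. Nor do they support a claim about which arm would be affected more. This is a cheap improvement to secondary, descriptive reporting and does not touch the primary analysis.

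**What to change.** 1. In SAP 6.2.1 and 6.2.1.1, base the post-baseline resistance endpoints on all participants with a post-baseline genotype or phenotype result: confirmed rebounders plus discontinuers tested under Protocol 7.1. Show counts by arm and route of entry, and state the denominator. Align Protocol 9.4.3.2 and SAP 6.2.2.2.1.
2. Keep confirmed rebound as the endpoint. Add one supportive row for participants whose last available value was ≥200 copies/mL and unconfirmed at discontinuation.
3. State in SAP 2.4.1.1 that ESID HIV-1 RNA and resistance samples count for these analyses although drawn after the last dose. Without this, the first two changes could be undone by the cut-off.

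The cost is some wording and one or two table rows. No sample, test or clinical procedure changes. The downside is that a few isolated elevations may be counted in the supportive row, so the figures may look slightly less favourable.

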3. OBJECTIVES AND ENDPOINTS

3.1. Week 24 Objectives and Endpoints

Objectives	Endpoints					
Primary						
To assess the percent change in body weight when switching to D/C/F/TAF FDC (Immediate Switch Arm) compared to continuing the current INI + TAF/FTC ARV regimen (Delayed Switch Arm) in virologically-suppressed (HIV-1 RNA <50 copies/mL) HIV-1 infected participants who have experienced rapid and significant body weight gain Secondary	Percent change from Baseline in body weight at Week 24					
Metabolic						
To assess changes in body weight when switching to D/C/F/TAF FDC (Immediate Switch Arm) compared to continuing the current INI + TAF/FTC ARV regimen (Delayed Switch Arm)	 Change from Baseline in absolute body weight at Week 24 Proportion of participants with % change in body weight >3% at Week 24 Proportion of participants with % change in body weight >5% at Week 24 Change from Baseline in BMI at Week 24 					
To assess changes in body composition when switching to D/C/F/TAF FDC (Immediate Switch Arm) compared to continuing the current INI + TAF/FTC ARV regimen (Delayed Switch Arm)	Change from Baseline in body composition as measured by DEXA scan at Week 24 Change from Baseline in waist circumference at Week 24					
To assess change in blood pressure when switching to D/C/F/TAF FDC (Immediate Switch Arm) compared to continuing the current INI + TAF/FTC ARV regimen (Delayed Switch Arm)	Change in SBP and DBP from Baseline at Week 24					
To assess changes in clinical laboratory tests when switching to D/C/F/TAF FDC (Immediate Switch Arm) compared to continuing the current INI + TAF/FTC ARV regimen (Delayed Switch Arm)	 Change from Baseline in fasting lipids at Week 24 Change from Baseline in fasting glucose at Week 24 Change from Baseline in HOMA-IR at Week 24 Change from Baseline in HbA1c at Week 24 Change from Baseline in leptin and adiponectin at Week 24 					
To assess changes in liver biomarkers when switching to D/C/F/TAF FDC (Immediate Switch Arm) compared to continuing the current INI + TAF/FTC ARV regimen (Delayed Switch Arm)	 Change from Baseline in the proportion of participants with advanced fibrosis according to the NAFLD fibrosis score at Week 24 Change from Baseline in the proportion of participants at high risk of NASH according to the HAIR score at Week 24 					

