To evaluate adherence in participants switching to D/C/F/TAF FDC (Immediate Switch Arm)	 Adherence rates by participant self-report using 4-day recall at Weeks 36 and 48
Exploratory	
Exploratory clinical biomarker	
To assess changes in alpha melanocyte-stimulating hormone when switching to D/C/F/TAF FDC (Immediate Switch Arm)	Change from Baseline in alpha melanocyte-stimulating hormone at Week 48
Exploratory PROs	
To assess changes in eating-related concepts (hunger, appetite, cravings, and satiety) for participants switching to D/C/F/TAF FDC (Immediate Switch Arm)	Change from Baseline in the scores on the DAILY EATS at Week 48
To assess changes in concerns about body shape for participants switching to	• Change from Baseline in the scores on the BSQ-8D at Week 48

CONFIDENTIAL – FOIA Exemptions Apply in U.S.

Objectives	Endpoints
D/C/F/TAF FDC (Immediate Switch Arm)	• Change from Baseline in the proportion of participants who have no concern (<19), mild concern (19-25), moderate concern (26-33) or marked concern (>33) with their body shape on the BSQ-8D at Week 48

Abbreviations: AE: adverse event, ARV: antiretroviral, BMI: body mass index, BSQ 8D: body shape questionnaire, D/C/F/TAF FDC: Darunavir/Cobicistat/Emtricitabine/Tenofovir Alafenamide Fixed dose Combination, DBP: diastolic blood pressure, DEXA: dual energy X ray absorptiometry, FDA: Food Drug Administration, FTC: emtricitabine, HAIR: hypertension, age, insulin, resistance, HIV 1 RNA: human immunodeficiency virus type 1 ribonucleic acid, HIV SI: HIV Symptom Index, HOMA IR: homeostatic model assessment of insulin resistance, INI: integrase, NAFLD: non alcoholic fatty liver disease, NASH: Nonalcoholic fatty liver disease, PGIC: patient global impression of change, PR: protease, PROs: patient reported outcomes, RT: reverse transcriptase, SAE: serious adverse event, SBP: systolic blood pressure.

3.3. Consistency of Effect of Baseline to Week 24 (Immediate Switch) versus Week 24 to Week 48 (Delayed Switch)

Additional secondary objectives/endpoints will evaluate the consistency of effect on outcomes from Baseline to Week 24 in the Immediate Switch Arm versus the Week 24 to Week 48 in the Delayed Switch Arm. The endpoints for the Delayed Switch Arm from Week 24 to Week 48 are the same as for the Immediate Switch to Week 24. Comparison will be made descriptively to evaluate the consistence of outcomes between these two arms for each endpoint.

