- Change from Baseline in the proportion of participants who have no concern (<19), mild concern (19-25), moderate concern (26-33) or marked concern (>33) with their body shape on the BSQ-8D at Week 24 and Week 48, respectively.

6.2.1.1. Consistency of Effect of Baseline to Week 24 (Immediate Switch) versus Week 24 to Week 48 (Delayed Switch)

Metabolic:

- Change in absolute body weight from Baseline to Week 24 (Immediate Switch Arm) compared to the change in absolute body weight from Week 24 to Week 48 (Delayed Switch Arm)
- The proportion of participants having a >5% change in body weight from Baseline to Week 24 (Immediate Switch Arm) compared to the proportion of participants having a >5% change in body weight from Week 24 to Week 48 (Delayed Switch Arm)
- The proportion of participants having a >3% change in body weight from Baseline to Week 24 (Immediate Switch Arm) compared to the proportion of participants having a >3% change in body weight from Week 24 to Week 48 (Delayed Switch Arm)
- Change in BMI from Baseline through Week 24 (Immediate Switch Arm) compared to the change in BMI from Week 24 through Week 48 (Delayed Switch Arm)
- Change in BMI categories from Baseline through Week 24 (Immediate Switch Arm) compared to the change in BMI categories from Week 24 through Week 48 (Delayed Switch Arm)
- Percent change in body weight from Baseline to Week 24 (Immediate Switch Arm) compared to the percent change in body weight from Week 24 to Week 48 (Delayed Switch Arm).
- Percent change in Visceral Adipose Tissue from Baseline to Week 24 (Immediate Switch Arm) compared to the percent change in Visceral Adipose Tissue from Week 24 to Week 48 (Delayed Switch Arm).
- Change in body composition as measured by DEXA from Baseline through Week 24 (Immediate Switch Arm) compared to the change in body composition from Week 24 through Week 48 (Delayed Switch Arm)
- Change in waist circumference from Baseline to Week 24 (Immediate Switch Arm) compared to the change in waist circumference from Week 24 to Week 48 (Delayed Switch Arm)
- The proportion of participants having a waist circumference of > 40 inches for men and > 35 inches for women at Week 24 (Immediate Switch Arm) compared to the proportion of participants having waist circumference of > 40 inches for men and > 35 inches for women at Week 48 (Delayed Switch Arm)

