- Change in SBP and DBP from Baseline to Week 24 (Immediate Switch Arm) compared to the change in SBP and DBP from Week 24 to Week 48 (Delayed Switch Arm)
- Change in fasting lipids from Baseline to Week 24 (Immediate Switch Arm) compared to the change in fasting lipids from Week 24 to Week 48 (Delayed Switch Arm)
- Change in fasting glucose from Baseline to Week 24 (Immediate Switch Arm) compared to the change in fasting glucose from Week 24 to Week 48 (Delayed Switch Arm)

- Change in in HOMA-IR from Baseline to Week 24 (Immediate Switch Arm) compared to the change in HOMA-IR from Week 24 to Week 48 (Delayed Switch Arm)
- Change in HbA1c from Baseline to Week 24 (Immediate Switch Arm) compared to the change in HbA1c from Week 24 to Week 48 (Delayed Switch Arm)
- Change in leptin and adiponectin from Baseline to Week 24 (Immediate Switch Arm) compared to the change in leptin and adiponectin from Week 24 to Week 48 (Delayed Switch Arm)
- Change in the proportion of participants from Baseline to Week 24 with advanced fibrosis according to the NAFLD fibrosis score (F0-F1, Indeterminate, and F3-F4) (Immediate Switch Arm) compared to the change in the proportion of participants from Week 24 to Week 48 with advanced fibrosis according to the NAFLD fibrosis score (Delayed Switch Arm)
- Change in the proportion of participants from Baseline to Week 24 at high risk of NASH according to the HAIR score (<2 and ≥2) (Immediate Switch Arm) compared to the change in the proportion of participants from Week 24 to Week 48 at high risk of NASH according to the HAIR score (Delayed Switch Arm)
- Proportion of participants having a dose-reduction or complete withdrawal of anti-hypertensive, anti-hyperglycemic, or lipid lowering agents from Baseline to Week 24 (Immediate Switch Arm) compared to Week 24 to Week 48 (Delayed Switch Arm)
- Proportion of participants starting an anti- hypertensive, anti-hyperglycemic, or lipid lowering agent from Baseline to Week 24 (Immediate Switch Arm) compared to Weeks 24 to Week 48 (Delayed Switch Arm)

Safety:

- Incidence of any Grade AEs (related and not related) through Week 24 (Immediate Switch Arm) compared to the incidence of any grade AEs (related and not related) through Week 48 (Delayed Switch Arm)
- Incidence of Grade 3 and 4 AEs (related and not related) through Week 24 (Immediate Switch Arm) compared to the incidence of Grade 3 and 4 AEs (related and not related) through Week 48 (Delayed Switch Arm)

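### The waist-threshold consistency endpoint in SAP 6.2.1.1 compares end-of-period proportions, so it does not isolate the change since the switch

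*SAP*

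**What the plan says.** Protocol 3.3 gives the purpose of these comparisons: to "evaluate the consistency of effect on outcomes from Baseline to Week 24 in the Immediate Switch Arm versus the Week 24 to Week 48", the second period being that of the Delayed arm. It adds that "Comparison will be made descriptively to evaluate the consistence of outcomes between these two arms for each endpoint". SAP 6.2.1.1 carries the same two periods in its title.

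The waist-threshold item in that section takes, for the Immediate arm, "The proportion of participants having a waist circumference of > 40 inches for men and > 35 inches for women at Week 24". For the Delayed arm it takes the proportion above the same limits, "inches for men and > 35 inches for women at Week 48 (Delayed Switch Arm"). Baseline does not enter for the Immediate arm, and Week 24 does not enter for the Delayed arm.

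Its neighbours are built differently:

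- The item just before it reads "Change in waist circumference from Baseline to Week 24 (Immediate Switch Arm) compared to the change in waist circumference from Week 24", where the Delayed arm's period again ends at Week 48, so continuous waist is compared as a change.
- The HAIR item, also a threshold proportion, begins "Change in the proportion of participants from Baseline to Week 24 at high risk of NASH according to the HAIR score". The NAFLD fibrosis, HIV-SI and BSQ-8D proportions follow the same pattern.

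The protocol's own waist endpoint is "Change from Baseline in waist circumference at Week 24" (Protocol 3.1). It lists no waist-threshold proportion. SAP 6.2.2.1 limits secondary metabolic endpoints to descriptive statistics and frequency tables.

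**The concern.** The section asks whether switching does the same thing in the two arms. For a threshold proportion, that means comparing how far each arm moves from its own pre-switch visit. The item as written compares where each arm ends up.

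The two arms do not start their periods from the same place. The Immediate arm starts at randomised Baseline. The Delayed arm starts at Week 24, after 24 more weeks on INI + TAF/FTC. Waist may have moved in that time, and some participants may have left. The trial's own hypothesis is that weight behaves differently on the two regimens, so equal starting prevalence cannot be taken for granted.

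At stake is how one table is read. It could suggest that the effect was not reproduced when it was, or that it was reproduced when it was not.

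**Working it through.** **Inputs.** From the documents: 1:1 allocation with 55 per arm (SAP 1.5), the two periods (Protocol 3.3), and the endpoint as worded in SAP 6.2.1.1. The documents give no waist prevalence, no drift on the INI regimen and no effect of switching on prevalence. Values for these below are assumptions.

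**The plan's own figure.** No figure is given for this endpoint. The 55 per arm belongs to the primary endpoint and reproduces with the plan's formula: 16/ES² = 16/0.54² = 54.87, rounded up to 55.

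**Decomposition.** Let S be the proportion above the threshold at the start of an arm's period, C the change during it, and L = S + C the level at the end. With I for Immediate and D for Delayed:

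L_D − L_I = (S_D − S_I) + (C_D − C_I)

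The SAP reports the left-hand side. The section's question concerns only C_D − C_I. A starting gap S_D − S_I therefore enters one-for-one.

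**Illustration.** Assume 60% prevalence at Baseline in both arms, and drift of 0 to 10 points in the Delayed arm by Week 24. In the first three rows switching lowers prevalence by 10 points in both arms. In the last row it does so by 10 points (Immediate) and 20 points (Delayed).

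| Case | Immediate, Baseline → Week 24 | Delayed, Week 24 → Week 48 | Gap in levels | Gap in changes |
|---|---|---|---|---|
| Same effect, no drift | 60 → 50 | 60 → 50 | 0 | 0 |
| Same effect, drift +5 | 60 → 50 | 65 → 55 | +5 | 0 |
| Same effect, drift +10 | 60 → 50 | 70 → 60 | +10 | 0 |
| Different effect, drift +10 | 60 → 50 | 70 → 50 | 0 | −10 |

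Rows 2 and 3 show an apparent inconsistency where there is none. Row 4 hides a real one.

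**Chance part of the starting gap.** With 55 per arm and assumed prevalence p, the standard error is √(2p(1−p)/55):

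- p = 0.5: √(0.50/55) = 9.5 points
- p = 0.7: √(0.42/55) = 8.7 points

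The 95% range is about ±17 to ±19 points. This is sampling spread only. It does not estimate the drift.

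**Comparison with the sibling items.** All the other metabolic items in SAP 6.2.1.1 are either a change over the period or an event within it, such as starting a medication. The waist-threshold item is the only one written as an end level.

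**The case against.** The strongest reply is that the waist question is already answered properly. The preceding item compares change in continuous waist circumference since the switch, and BMI, percent weight change, visceral fat and DEXA are handled the same way. A reader will see those beside the threshold proportion, which is an extra, untested summary with no margin or decision rule. An attained level is also a legitimate thing to report, and the virologic snapshot items in the same section are levels. Baseline waist is summarised by arm (SAP 4.1, Table 3), and waist category is a subgroup for the baseline tables (SAP 2.5), so a Baseline imbalance would probably be visible.

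Most of this stands and limits the reach of the point. Two parts do not remove it. The virologic items start from near-uniform suppression, because eligibility requires HIV-1 RNA below 50 copies/mL at screening. No eligibility criterion concerns waist. And the value most needed, the Delayed arm's Week 24 proportion above the threshold, is not among the listed outputs.

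Three stronger readings are tempting and are not supported:

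- A reader might infer that the waist consistency assessment as a whole is faulty. The continuous item shows otherwise.
- A reader might take the standard errors above as the size of a bias. They are sampling precision on assumed prevalences, and randomisation balances Baseline in expectation.
- A reader might see the differing cut-offs (strictly above 40/35 inches here, at or above in SAP 2.5) as a second substantive flaw. They affect only values exactly on the line.

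**Conclusion.** The item is wrong as written, but the matter is minor. It does not measure change since the switch, and any difference between the Immediate arm's Baseline and the Delayed arm's Week 24 prevalence enters it in full. That follows from the wording and needs no assumption. The size of the distortion is unknown: the 0 to 10 points illustrated rest on assumed prevalence, drift and effect.

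The consequence is confined to one secondary, descriptive, SAP-only summary. Nothing in the documents lets it reach the primary comparison of percent weight change, the control of alpha or the sample size.

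**What to change.** In SAP 6.2.1.1, restate the item as the change in the proportion above the waist threshold, Baseline to Week 24 (Immediate) against Week 24 to Week 48 (Delayed). Add a shift table for each arm from the participant's own pre-switch visit, restricted to those measured at both ends, so that dropout does not masquerade as change. The end levels can still be shown, provided that the starting proportions stand next to them.

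As a tidy-up, choose either strictly above or at-or-above for the 40/35-inch limits and use it both here and in SAP 2.5.

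The cost is SAP wording and one table shell. The Schedule of Activities already has waist measured at Baseline, Week 24 and Week 48, so no new data are needed.
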